A recent review and meta-analysis of these new oral anticoagulants has concluded that they were equally as good as enoxaparin but did have a higher bleeding tendency. The drugs did not differ significantly for efficacy and safety. (24)

NOACs do not require routine coagulation monitoring and seem to be the way of the future for ease of administration efficacy and tolerability. Additional research is needed to determine how these new oral anticoagulants should be used in special populations such as the obese medical or surgical patient.

[figure not shown]

Figure 1 Mechanism of Action of Anticoagulants

*Derived from Dwek et al 2012

4. Study Procedures

a. Study design, including the sequence and timing of study procedures

Patients will be recruited from our preoperative bariatric surgical clinic (Roux-en Y gastric bypass, and vertical sleeve gastrectomy). Each patient will undergo a thorough history and physical exam (routine standard of care for bariatric patients) to document demographics including: age, sex, height, weight, body mass index and absence of the exclusion criteria. See Table 1 for sequence and timing of study procedures.

Table 1. Sequence and Timing of Study Procedures

Overview of Study Visits: Specific Aims 1, 2 and 3							
Study Visit Before and After Intervention		Specific Aim 1 Specific Aim 2		Specific Aim 3			
		Pharmacokinetics (Prior to Surgery)	Pharmacokinetics (Following Surgery)	Pharmacodynamics			
1	3 to 5 Weeks Prior to Bariatric Surgery (study participant receives one 5 mg dose of apixaban)	х		х			
2	1 Month (4 to 6 weeks) Post-bariatric surgery (study participant receives one 5 mg dose of apixaban)		x	x			
3	6 Months (6 to 8 months) Post-bariatric surgery (study participant receives one 5 mg dose of apixaban)		x	х			
4	12 Months (12 to 14 months) Post-bariatric surgery * (study participant receives one 5 mg dose of apixaban)		x	х			
5	Final Exit Interview Visit (two weeks following final visit)	Review any adverse events that may have occurred throughout entire study					

Note: Research participants in each group (RYGB, n=15; VSG, n=15; Total n=30) will undergo the study protocol detailed above.

*The patient ideally will have lost at least 30% to 50% of excess body weight by 12 months

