To determine the durability or change in pharmacokinetics and pharmacodynamics of apixaban in patients with a body mass index (BMI) of 35 kg/m² or greater following one of two bariatric surgical procedures (pre-operative versus post-operative vertical sleeve gastrectomy or Roux-en-Y gastric bypass patients).

b. Secondary outcome variables.

1. To compare/contrast the pharmacokinetics and pharmacodynamics of apixaban in bariatric surgical patients who have undergone RYGB vs. VSG.

2. To determine how the pharmacokinetics of the drug may differ when there is significant post-operative surgical weight loss (>40% estimated excess body weight) 12 months following surgery versus those patients who have suboptimal weight loss following bariatric surgery (< 40% of estimated excess body weight).

c. Statistical plan including sample size justification and interim data analysis.

We propose to study 15 subjects in each arm (RYGB vs. VSG) and use them as their own controls. We have accounted for loss to follow-up (even with a 36% (5 in each group) drop-out rate, we would have enough subjects (10 per group) to demonstrate a 36 % change in AUC with an alpha error of 0.05 and a beta error of 0.2 (Power of 80%). If there is no loss to follow-up and all patients remain in the study, this will allow us to demonstrate a 29% change in AUC with an alpha error of 0.05 and a beta error of 0.2.

These calculations were calculated based on the following data from Upreti et al.: Ratio of geometric mean point estimated for high body weight (>120 kg) vs. normal body weight for C_{max} = 0.692 (0.586, 0.818) and AUC (INF) = 0.77 (0.652, 0.912).

Routine pharmacokinetic data will be determined, including C_{max}, T_{max} and AUC for each subject at each dosing time, and compared within subjects and between subjects and between groups. Factor Xa activity will be compared to apixaban concentration at each time point.

d. Early stopping rules.

While we do not expect to have any serious adverse events related to the administration of a single dose of 5 mg of apixaban as required in this study, we will interrupt the study and report to the IRB if 10% or more of our first 12 subjects suffer a serious adverse event "definitely

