related" or "probably related" to the administration of apixaban. In such a case, we will not resume the study until the investigators, the sponsor, and the IRB are satisfied that there are alternative explanations for the events not related to apixaban, or the study procedures are altered to reduce the risk of such events for future participants. After the first 20 subjects, if there is ever a point where 10% or more of the subjects suffer a serious adverse event either "definitely" or "probably" related to apixaban, the same approach will be taken.

8. Risks

a. Medical risks, listing all procedures, their major and minor risks and expected frequency.

The only risks related to pharmacokintectic and pharmacodynamics studies are minor bleeding and/or bruising at the IV insertion site and the possibility of vasovagal reactions to blood draws.

The risks associated with use of apixaban are as follows:

Bleeding: As with other anticoagulants, subjects administered with apixaban are to be carefully observed for signs of bleeding.

Stroke: Stroke has been reported occasionally in studies of apixaban (multiple dosing studies). However, given that this is a single dose study – the likelihood of such a complication is rare. As part of good clinical practice, the investigators will remain vigilant.

b. Steps taken to minimize the risks.

To minimize the risks we will use experienced phlebotomists from the CRU to place the venous catheters for blood drawing or to draw the blood via venipuncture if preferred by the subject. Those drawing the blood will be familiar with the possibility of vasovagal reactions, and will have the subject lay down with legs elevated if the subject becomes symptomatic. The patients will be monitored for a full 24 hours after ingesting the single dose of apixaban. The participant will then return at 48 hours and at 72 hours at which time we can check in with the patient and ensure there are no side effects to the medication or complications. We will also closely monitor subjects before, during, and after study visits.

All records will be secured in research offices. Computers that contain patient data are password protected.

WOMEN OF CHILD-BEARING POTENTIAL (WOCBP)

Sexually active Women of Child-Bearing Potential (WOCBP) must use an effective method of birth control during the course of the study, in a manner such that risk of failure is minimized.

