Before study enrollment, WOCBP must be advised of the importance of avoiding pregnancy during study participation and the potential risk factors for an unintentional pregnancy. The subject must sign an informed consent form documenting this discussion.

All WOCBP MUST have a negative pregnancy test within 24hours before receiving apixaban. The minimum sensitivity of the pregnancy test must be 25 IU/L or equivalent units of HCG. If the pregnancy test is positive, the subject must not receive apixaban and must not be enrolled in the study.

In addition, all WOCBP should be instructed to contact the investigator immediately if they suspect they might be pregnant (e.g., missed or late menstrual period) at any time during study participation.

ADVERSE EVENT REPORTING

All Serious Adverse Events (SAEs) that occur following the subject's written consent to participate in the study through 30 days of discontinuation of dosing must be reported to Bristol Meyers Squibb (BMS) Worldwide Safety.

Adverse Events

- An Adverse Event [AE] is defined as any new untoward medical occurrence or worsening of a pre-existing medical condition in a patient or clinical investigation subject administered an investigational (medicinal) product and that does not necessarily have a causal relationship with this treatment. An AE can therefore be any unfavorable and unintended sign (including an abnormal laboratory finding, for example), symptom, or disease temporally associated with the use of investigational product, whether or not considered related to the investigational product.
- The causal relationship to study drug is determined by a physician and should be used to assess all adverse events (AEs). The causal relationship can be one of the following:
 - Related: There is a reasonable causal relationship between study drug administration and the AE.
 - Not Related: There is not a reasonable causal relationship between study drug administration and the AE.
- The term "reasonable causal relationship" means there is evidence to suggest a causal relationship.
- Adverse events can be spontaneously reported or elicited during open-ended questioning, examination, or evaluation of a subject. (In order to prevent reporting bias, subjects should not be questioned regarding the specific occurrence of one or more adverse events).

Serious Adverse Events

A Serious Adverse Event (SAE) is any untoward medical occurrence at any dose that:

- results in death

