- is life-threatening (defined as an event in which the subject was at risk of death at the time of the event; it does not refer to an event which hypothetically might have caused death if it were more severe)

- requires inpatient hospitalization or causes prolongation of existing hospitalization (see **NOTE***: below for exceptions)
- results in persistent or significant disability/incapacity
- is a congenital anomaly/birth defect
- is an important medical event, defined as a medical event that may not be immediately lifethreatening or result in death or hospitalization but, based on appropriate medical and scientific judgment, may jeopardize the subject or may require intervention (e.g., medical, surgical) to prevent one of the other serious outcomes listed above. Examples of such events include but are not limited to intensive treatment in an emergency department or at home for allergic bronchospasm; blood dyscrasias or convulsions that do not result in hospitalization.
- Suspected transmission of an infectious agent (eg, pathogenic or non-pathogenic) via the study drug is an SAE.

Although pregnancy, overdose, and cancer are not always serious by regulatory definition, these events must be handled as SAEs.

Adverse Events of Special Interest

In this study, the following adverse events are to be reported to BMS, regardless of whether these reports are classified as serious or unexpected.

- Potential or suspectived cases of liver injury including but not limited to liver test abnormalities, jaundice, hepatitis or cholestasis.

***NOTE:** The following hospitalizations are not considered SAEs:

- A visit to the emergency room or other hospital department lasting less than 24 hours that does not result in admission (unless considered an "important medical event" or a life-threatening event)
- Elective surgery planned before signing consent
- Admissions as per protocol for a planned medical/surgical procedure
- Routine health assessment requiring admission for baseline/trending of health status (eg, routine colonoscopy)
- Medical/surgical admission other than remedying ill health state that was planned before study entry. Appropriate documentation is required in these cases
- Admission encountered for another life circumstance that carries no bearing on health status and requires no medical/surgical intervention (eg, lack of housing, economic inadequacy, caregiver respite, family circumstances, administrative reason)

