The study does not have funding to pay for any medical complications of study participation. The participants would therefore assume the potential financial risk of unanticipated medical care costs.

9. Benefits

a. Description of the probable benefits for the participant and for society. There may be no benefit to the participant. Potential benefits to society include improved knowledge about prophylaxis with oral anticoagulation medications during bariatric surgery and following surgery when treating a prior bariatric surgical patient with an oral anticoagulation medication for a medical condition such as stroke or atrial fibrillation.

10. Payment and Remuneration

a. Detail compensation for participants including possible total compensation, proposed bonus, and any proposed reductions or penalties for not completing the protocol.

To compensate patients for their time and participation - \$250.00 plus a parking pass will be given per visit completed:

Visit 1: **Pre-op**: 24 hours inpatient/48 hour blood draw outpatient/72 hour blood draw outpatient \$250.00 completed visit

Visit 2: **1 month**: 24 hours inpatient/48 hour blood draw outpatient/72 hour blood draw outpatient \$250.00 completed visit

Visit 3: **6 month**: 24 hours inpatient/48 hour blood draw outpatient/72 hour blood draw outpatient \$250.00 completed visit

Visit 4: **12 month**: 24 hours inpatient/48 hour blood draw outpatient/72 hour blood draw outpatient \$250.00 completed visit

Final Exit Interview by telephone (two weeks following visit #4): Review any adverse events that may have occurred. No compensation at this time.

The total amount of compensation possible is \$1,000.00 plus parking.

11. Costs

a. Detail costs of study procedure(s) or drug (s) or substance(s) to participants and identify who will pay for them.

No costs to the participants.

Table 3. Timeline for Study

	Year 1				Year 2			
TASK	July 2016	Oct. 2016	Jan. 2017	April 2017	July 2017	Oct. 2016	Jan. 2018	April 2018
Submission of Grant to BMS								

and Organization of Study				
Materials and supplies				
Database creation/testing				
JHU IRB approval				
Recruitment and enrollment				
Data collection				
Enter and clean data				
Data quality review				
Analyze data				
Abstract submissions				
Manuscript preparation				
Preparation of other grants				

References

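### Section 7d pools all related serious adverse events under one 10% share, so a single related death or life-threatening event among the first 12 subjects does not trigger interruption or joint review

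*Combined protocol and SAP*

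**What the plan says.** Section 7d (Early stopping rules) has two parts. The first is "we will interrupt the study and report to the IRB if 10% or more of our first 12 subjects suffer a serious adverse event" that is definitely or probably related to apixaban. The second begins "After the first 20 subjects, if there is ever a point where 10% or more of the subjects suffer a serious adverse event" and has the same causality condition and consequence. Once interrupted, the study resumes only when the investigators, the sponsor and the IRB accept that apixaban was not the explanation, or when procedures have been changed to lower the risk.

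The same section states that "we do not expect to have any serious adverse events related to the administration of a single dose of 5 mg of apixaban". Section 9a adds: "There may be no benefit to the participant". The note to Table 1 gives the planned size as "RYGB, n=15; VSG, n=15; Total n=30", with one dose at each of four visits.

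The SAE definition in Section 8 lists several kinds of event. One entry is "results in death"; another begins "is life-threatening (defined as an event in which the subject was at risk of death at the time of the event". Inpatient hospitalization is in the same list. Section 7d uses the pooled term and gives no entry separate weight.

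**The concern.** The whole study-level safeguard rests on a percentage of a small number of subjects. With 12 subjects, 10% is 1.2 people, so the first look needs two affected subjects whatever happened to them. A related hospitalization and a related death count the same.

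Participants take the drug for research purposes, with no expected benefit and no expected related SAE. If one of them had a related fatal event, the written plan would let dosing of up to 30 − 1 = 29 others go on without calling for the IRB report and joint review in 7d. The protocol already treats fatal and life-threatening events separately when it sets reporting times, but that distinction does not reach the interruption rule.

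**Working it through.** **Inputs.** The threshold (10% or more), the first look (12 subjects) and the later looks (any point after the first 20) come from Section 7d. The planned total of 30 comes from Table 1. The plan states no event count or operating characteristic for this rule, so there is no figure of its own to reproduce.

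**Formula.** With r affected subjects among n, the rule triggers when r/n ≥ 0.10.

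| n | r | r/n | 10% reached? |
|---|---|---|---|
| 12 | 1 | 8.3% | no |
| 12 | 2 | 16.7% | yes |
| 20 | 1 | 5.0% | no |
| 20 | 2 | 10.0% | yes, if 20 is itself a look |
| 21 | 2 | 9.5% | no |
| 30 | 2 | 6.7% | no |
| 30 | 3 | 10.0% | yes |

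The smallest triggering count is 2 at n = 12, 2 at n = 20, and 3 at every n from 21 to 30.

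**Two affected subjects.** Whether the rule triggers depends on where they fall, counting events in order of subject entry:
- Both in the first 12: 2/12 = 16.7%, triggered.
- Both in the first 20 but not both in the first 12: 2/20 = 10.0%, triggered only if the 20-subject point is a look. If the first later look is at 21, 2/21 = 9.5% and the rule is not triggered.
- At least one from subject 21 onwards: at most 9.5%, not triggered at any n up to 30.

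**Does another section supply a study-level pause?**
- Section 4f removes a participant who has a significant illness or a major bleed put down to apixaban. It acts on that person only.
- Section 8, on SAE collecting and reporting, requires a report to the supporting company within 24 hours. No pause is attached.
- Section 8, on health authority reporting, sets 7 days for a death or life-threatening event and 15 days for other SAEs, for studies under an investigator-sponsored IND. Again no pause is attached.

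**Two inconsistencies in the same rule.**
- Section 7d counts events as definitely or probably related. The adverse event definitions in Section 8 allow only Related or Not Related, so the recorded assessment does not map onto the rule.
- No look is stated between the first 12 and the first 20. Two affected subjects would be at least 10% at every n from 13 (2/13 = 15.4%) to 20 (2/20 = 10.0%), but unless both are in the first 12, no part of 7d clearly applies.

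**The case against.** The best defence is that the rule is coherent as written. It counts only serious events, so it is not blind to severity. The documents point to low risk: a single 5 mg dose per visit, far larger doses described in Section 6c as tolerated by healthy volunteers, 24 hours of inpatient monitoring with checks at 48 and 72 hours, and exclusion of people with active bleeding or on anticoagulants. A physician assesses causality for every event, and every SAE reaches the supporting company within 24 hours. Nothing stops the investigators, the supporting company or the IRB from pausing on their own judgement. The IRB's own event-reporting policy is not among the documents.

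Most of this stands, and it limits the point. A reader might infer that the rule ignores severity altogether; it does not, it only fails to distinguish among SAEs. A reader might infer that nobody would review a related death; the documents support only that 7d would not require its IRB report or joint review. A reader might also infer that any two related deaths among 21 or more subjects would pass; that depends on where they fall, as shown above. Finally, a reader might judge the rule by its chance of triggering at some assumed SAE risk. The documents give no such risk, and the result would describe the pooled rule, not the gap for fatal events.

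What the defence does not answer is the single-event case. It needs no condition on order, and no other section covers it. Discretion to pause is not a written requirement to do so. Reading 7d as a running rate, under which one event would reach 10% at 10 or fewer subjects, does not help either, because the text fixes the first look at 12.

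**Conclusion.** The point holds in a limited form. One related death or life-threatening SAE among the first 12 subjects (8.3%) does not trigger 7d. Two among 21 to 30 subjects (9.5% to 6.7%) do not either, unless both fell in the first 12, or in the first 20 if that count is a look. No other provision requires a study-level pause.

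This concerns what the written rule requires, not what the investigators or IRB would in fact do. It assumes that the first look uses 12 as a fixed denominator and that each subject counts once. It is a gap in participant protection and does not affect the pharmacokinetic analysis. A change is worth making because the rule fits poorly with the protocol's own expectation of no related SAE and possibly no participant benefit.

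**What to change.** Reconcile Section 7d with the fatal and life-threatening categories in Section 8 (the SAE definition and health authority reporting), so that for those categories the existing interruption and joint review no longer rest solely on the pooled 10% share. The sponsor, the investigators and the IRB should set the exact trigger; this review does not propose one. The 10% rule can stay for SAEs in general.

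In the same edit:
- use one causality scale in 7d and in the adverse event definitions, or state how one maps to the other;
- state how subjects 13 to 20 are covered, and whether the 20-subject point is itself a look.

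The cost is a few sentences in 7d and a possible short pause after an event that the protocol does not expect. The SAE categories needed are already defined.

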Combined P- glycoprotein and strong CYP 3A4 inhibitor	boceprevir, cobicistat, conivaptan, delavirdine, diltiazem, dronedarone, all HIV protease inhibitors (eg. ritonavir), imatinib,indinavir,itraconazole,ketoconazole, nefazodone, posaconazole, telaprevir, telithromycin, voriconazole	Significant increase in apixaban levels and increased potential for bleeding complications	AVOID USE. Risk higher with renal impairment	
Combined P- glycoprotein and moderate CYP 3A4 inhibitor	amoidarone, azithromycin, chloramphenicol, cimetidine, erythromycin, clarithromycin, cyclosporin, diltiazem, dronedarone, felodipine, fluconazole, grapefruit, lapatinib, mifepristone, nicardipine, quinidine, ranolazine, tamoxifen, telithromycin, ticagrelor, verapamil	Moderate increase in apixaban levels in patients with normal renal function. Significant increase in apixaban levels in patients with severe renal function (CrCl < 30 ml/min)	Prescribe apixaban with caution in patients with normal renal function. AVOID USE in patients with severely impaired renal function (CrCl < 30 ml/min), age > 80 years or low body weight (< 60 kgs).	
Combined P- glycoprotein inducer and strong CYP 3A4 inducer	carbamazepine, dexamethsone, phenytoin, rifampin, St John's wort	Significant reduction in apixaban levels. Effects may persist for several weeks following discontinuation	AVOID USE	
Inducers of p- glycoprotein	doxorubicin, prazosin, tipranavir, trazodone, vinblastine	Significant reductionAVOID USEin apixaban levels.Effects may persist forseveral weeksfollowingdiscontinuationImage: Several		
Strong inducers of CYP 3A4	barbiturates, bosentan, efavirenz, etravirine, fosphenytoin, nafcillin, nevirapine, oxarbazepine, phenytoin, primidone, rifabutin, rifapentine	Significant reduction in apixaban levels. Effects may persist for several weeks following discontinuation	AVOID USE	

Drug Interactions with Apixaban: P-glycoprotein is a drug transporter that mediates apixaban absorption. P-glycoprotein inhibitors can increase apixaban absorption while inducers will reduce its absorption. The metabolism of apixaban is mediated by p450 liver microsomal enzyme CYP3A4. CYP3A4 inhibitors will increase apixaban levels while inducers will decrease levels.

b. Study duration and number of study visits required of research participants. Study duration: two years

Number of study visits: four (one month prior to surgery and 1, 6 and 12 months following surgery).

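### The section 7d stopping rule sets no study-level trigger for related SAEs between the first 12 and the first 20 subjects: a minor gap that is cheap to close

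*Combined protocol and SAP*

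**What the plan says.** Protocol section 7d (Early stopping rules) has two sentences that trigger a pause.

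- The first concerns the start of the trial: "we will interrupt the study and report to the IRB if 10% or more of our first 12 subjects suffer a serious adverse event" that is definitely or probably related to apixaban.
- The second concerns the later part: "After the first 20 subjects, if there is ever a point where 10% or more of the subjects suffer a serious adverse event" of the same kind, the same steps follow.

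The consequence of a trigger is firm: "In such a case, we will not resume the study until the investigators, the sponsor, and the IRB are satisfied" that there is another explanation or that the procedures have been made safer. The section opens with the expectation behind the rule: "we do not expect to have any serious adverse events related to the administration of a single dose of 5 mg of apixaban".

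Thirty subjects are planned (Table 1 note). Each receives a single 5 mg dose at each of four visits: "four (one month prior to surgery and 1, 6 and 12 months following surgery" (section 4b).

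**The concern.** The two sentences do not meet. The first is tied to the first 12 subjects, and the second begins after 20. For the subjects in between, the text gives no cumulative count that obliges a pause, although the same 10% level and the same action apply on both sides and no reason is given for a break.

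This is the protocol's only rule for interrupting the whole study. Section 4f removes individual participants, and the reporting text in section 8 sends SAEs to the drug supplier and the FDA. Neither halts dosing in other subjects. What is at stake is participant safety for a short stretch of enrolment. The pharmacokinetic and pharmacodynamic analyses are not affected.

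**Working it through.** **Inputs from the protocol.** The 10% level and the cut points of 12 and 20 are in section 7d, the total of 30 subjects and the visit windows in Table 1, and the two-year duration in section 4b. The protocol states no operating characteristics for the rule, so there is no figure to reproduce.

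**Step 1: the 10% level as counts.** With n subjects dosed, the smallest count at or above 10% is ceil(0.10 × n).

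- n = 12: 1.2, so 2 subjects (2/12 = 16.7%).
- n = 13 to 20: 2 subjects (2/13 = 15.4%, 2/19 = 10.5%, 2/20 = 10.0%).
- n = 21 to 30: 3 subjects (2/21 = 9.5% is too few; 3/30 = 10.0%).

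One case in the first 12 and one in subjects 13 to 19 therefore reaches the 10% level at every n from 13 to 19, and neither sentence applies. If the later sentence includes n = 20, the two cases trigger there. If it starts at n = 21, they no longer do, and a third is needed. This step needs no assumption.

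**Step 2: how often, under assumptions.** The protocol gives neither a related-SAE risk nor an enrolment pace. Assumed:

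- a per-subject risk of 1%, 2%, 5% or 10%, at most one qualifying SAE per subject, equally likely at each of the four doses;
- 30 subjects enrolled evenly over 9 months, no dropout;
- doses at months 0, 2.1, 7.9 and 13.9, which are the mid-windows of Table 1 with surgery about 4 weeks after Visit 1. The last dose falls at 9 + 13.9 = 22.9 months, which fits "Study duration: two years";
- the first-12 sentence stays open through those subjects' later doses.

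About 14 of the 30 × 4 = 120 planned doses are then given while n is 13 to 19. Simulation results, as a percentage of trials:

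| Assumed risk | 1% | 2% | 5% | 10% |
|---|---|---|---|---|
| 10% level first reached at n = 13–19 | 0.19 | 0.74 | 3.97 | 11.69 |
| of these, not caught by the first-12 sentence | 0.13 | 0.48 | 2.59 | 7.45 |
| Ever interrupted, later rule starts at n = 21 | 0.83 | 3.68 | 22.77 | 62.34 |
| Ever interrupted, n = 20 included | 0.97 | 4.08 | 23.85 | 63.26 |
| Ever interrupted, with the fix | 0.97 | 4.08 | 23.85 | 63.26 |
| Difference, fix minus n = 21 start (points) | 0.14 | 0.40 | 1.08 | 0.92 |

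Repeat simulations gave 2.1% to 2.6% at 5% risk and 6.2% to 7.5% at 10% risk for the second row, so the decimals should not be leaned on.

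**Step 3: length of the delay if n = 20 counts.** In the uncaught cases the pause comes on average 1.0 month, 3.3 subjects and 6.4 doses late. With 6-month enrolment the figures are 0.7, 3.5 and 6.8; with 10-month enrolment, 1.1, 3.3 and 6.4.

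**Step 4: sensitivity to when the risk falls.** Uncaught cases at 1%, 5% and 10% risk (9 months):

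- half the risk at dose 1: 0.3%, 5.6%, 14.5%;
- half the risk at dose 2: 0.1%, 1.7%, 4.7%;
- all the risk at dose 1 (upper limit): P(X₁₂ ≤ 1) − P(X₁₉ ≤ 1), where Xₙ is binomial with n subjects. At 5% this is 0.8816 − 0.7547 = 12.7%. At 1% and 10% it is 0.9% and 23.9%.

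In that same limit, with the later rule starting at n = 21, the share of trials that reach the level at n = 13 to 20 and are never interrupted is 0.9%, 2.8%, 7.4% and 6.5% at 1%, 2%, 5% and 10% risk.

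**The case against.** Four arguments carry weight.

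1. The later sentence can naturally be read as applying once 20 subjects have been dosed. Then 2/20 triggers, and the fix changes only the date of the pause. This stands, but the text does not settle whether n = 20 is in or out.
2. Risks of 5% to 10% run against the protocol's expectation of no related SAEs and its statement in section 6c that doses up to 50 mg were well tolerated. At 1% to 2%, uncaught cases occur in about 0.1% to 0.5% of trials. This stands, although a stopping rule exists for the case where the expectation is wrong.
3. The rule is staged and does not hold 10% at every n: one case among the first 10 subjects is already 10%, yet alone it does not meet the first-12 sentence. Where the stages lie is partly preference. This is fair, but it does not explain a break between two stages that share one level and one action.
4. Other safeguards continue: 24-hour observation and checks at 48 and 72 hours (section 8b), SAE reports to the supplier within 24 hours, and removal after a major bleed attributed to apixaban (section 4f). Nothing forbids an earlier discretionary pause. These limit the harm but do not require a pause.

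A reader might infer more than the documents support. Participants are not unmonitored in the gap, for the reasons in item 4. The upper-limit percentages in Step 4 are not central estimates, because they put all risk on the first of four doses spread over more than a year. Nor do the documents show that 12 or 20 is a slip for the other number. Finally, section 8 grades causality on two levels ("Related: There is a reasonable causal relationship between study drug administration and the AE") while section 7d speaks of definite or probable relation. It is tempting to count every related SAE towards section 7d, but that could widen the trigger, and it is not proposed here.

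**Conclusion.** The gap is in the current wording, and its existence rests on no assumption: at 15.4% to 10.5% no pause is required. Its weight is minor. If n = 20 counts, the pause is delayed by about a month and 6 to 7 doses. If the later rule starts at n = 21, a crossing can be lost, and the chance of ever interrupting the study moves by about 1 percentage point at most at risks of 1% to 10%.

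The one-point figure depends on risk being spread equally over the doses and would be larger if risk were concentrated at the first. The figures also depend on the first-12 sentence staying open at later doses, which the text does not say. If it is a single look when the twelfth subject is dosed, every case in the first row of the table is uncovered while n is 13 to 19, not just those in the second.

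**What to change.** In section 7d:

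- Keep the first-12 sentence and add *at any dose*, so that 2 or more of those 12 subjects trigger a pause whenever the events occur.
- Open the later sentence with *At any point after the first 12 subjects* in place of its present start after 20. Two subjects then trigger at n = 13 to 20, and three at n = 21 to 30.

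The first-12 sentence should not be dropped in favour of the 2-then-3 boundary alone. At 5% risk that would lower the chance of interruption from 22.77% (present text, n = 21 start) to 20.90%, because two late cases among the first 12 would no longer suffice.

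The cost is one phrase changed and one added, with a slightly higher chance of an early pause. Visits, sample size, SAE reporting and the PK/PD analysis stay as they are.
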